9 STATISTICAL CONSIDERATIONS

9.1 STATISTICAL HYPOTHESES

The aim of this study is to assess the feasibility and acceptability of the sleep GOALS intervention to identify the necessary adaptations for a larger efficacy/implantation study. We will not perform formal hypothesis testing.

9.2 SAMPLE SIZE DETERMINATION

The primary aim of the pilot RCT is to obtain estimates of feasibility and acceptability to guide the planning of a larger efficacy trial and finalize the intervention's content and delivery. With a sample size of 40 (20 in each group), we will have the ability to estimate 95% confidence intervals with acceptable precision (i.e., confidence interval width) of 0.31 for all feasibility and acceptability benchmarks for the entire sample and 0.44 for within-group estimates. As an exploratory aim, we will obtain estimates of variability for the change in diet, physical activity, sleep, and weight to guide sample size calculations for the larger trial.

9.3 POPULATIONS FOR ANALYSES

For primary outcomes related to feasibility, we will include all randomized participants. For primary outcomes related to intervention acceptability, we will include all participants randomized to the Sleep GOALS intervention. For secondary outcomes, we will include all randomized participants (i.e., intention-to-treat)

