Analysis Plan: The primary study objective is to assess the feasibility and acceptability of Sleep GOALS. We will assess the feasibility of the intervention by estimating rates of recruitment, retention, and engagement (i.e., weekly logins; modules completed; daily self-monitoring of diet, physical activity, and sleep; weekly monitoring of weight using point estimates (means or sample proportions) and 95% confidence intervals). We will assess acceptability by estimating satisfaction rates on various intervention components (≥ 4 Acceptability and Feasibility Questionnaire). Our benchmarks for feasibility are similar to those used in the original GOALS Lifestyle intervention. We will use a benchmark of 80% for all feasibility and acceptability measures. To assess the intervention's preliminary efficacy, we will calculate point estimates and confidence intervals for change in weight and PWR. We chose these weight measures as our secondary outcomes since they will be the primary outcome in the future R01. However, we will also explore changes in our proposed behavioral mediators, sleep, diet, and physical activity to inform power calculations for a fully powered study.

We will conduct an exploratory analysis to determine how potential covariates (e.g., parity, breastfeeding status, postpartum depression, race/ethnicity, relationship status, and employment status) impact the intervention's feasibility, acceptability, and preliminary efficacy. For example, in some studies, breastfeeding is associated with longer nocturnal sleep²⁻⁴, but shorter nocturnal sleep in other studies.⁵ Collecting data on breastfeeding and other covariates will provide preliminary data on how it impacts the intervention.

Domain	Measure, Method of Assessment	Benchmarks for Success
Feasibility (Primary Outcome)		
Recruitment/Enrollment	Total sample	40 participants in 12 months
	Demographics of sample	$\geq 30\%$ ethnic minority
Retention	Attrition Rates	$\leq 20\%$ loss to follow-up
Engagement	Modules completed	≥ 14 (~80%) modules completed within 16 weeks
	Weekly self-monitoring of diet, sleep, and physical activity weekly	≥ 14 (~80%) weeks, ≥ 1 day of monitoring
	Weekly weigh-ins	≥ 14 (~80%) weeks, ≥ 1 day of weigh-ins
	Total time logged in	
Acceptability (Primary Outcome)		
Acceptability	Acceptability of the intervention delivery; behavior change curricula; action plan; intervention platform	$\geq 80\%$ agree or totally agree with each
Preliminary efficacy (Secondary Outcome)		

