4 STUDY DESIGN

4.1 OVERALL DESIGN

This study will use a single-blind, parallel-arm RCT design. Participants will be randomized at a 1:1 ratio to Sleep GOALS intervention (n=20) or an education control group (n=20).

Sleep GOALS: We anticipate Sleep GOALS will be a 16-week intervention. However, the results of Aim 1 will determine the intervention length and core content. We will use a protocol [name] and colleagues developed to adapt TSC to an online format and integrate it with the GOALS lifestyle intervention.^{6,7} Briefly, in-person delivery of TSC has 3 components: 1) delivery of the core content, 2) providing tailored feedback, and 3) providing motivation and support. We will adapt the first component to an online format with 15-to-20-minute informational videos. The participants will view the material at their convenience, with new videos available weekly. The GOALS software will send weekly automated email reminders to review the new session materials. We will use a lifestyle coach to adapt the 2nd and 3rd components. Evaluating patient perspectives on the original GOALS lifestyle intervention found individualized lifestyle coaching, encouragement, and accountability helpful.⁸ The coach will be a master's level student in a health-related program (e.g., physical activity and health promotion, nutrition and dietetics, etc.) with experience in weight-management counseling. As described in Aim 1, the coach will assist with developing Sleep GOALS to familiarize them with the intervention content. However, the coach will complete a 2-day training workshop using a similar training format as the GOALS Lifestyle intervention.⁷ The coach will help participants develop an individualized sleep treatment plan based on their baseline sleep assessment. For example, coaches will encourage participants to document challenges for sleep (e.g., infant sleep, lack of partner support) and identify one treatment strategy they deem feasible to implement each week. The coach will monitor participant progress and engagement weekly to revise the sleep treatment plan, diet, and activity as needed. Coaches will provide personalized feedback and encourage accountability and re-engagement through a secure messaging system in the Sleep GOALS platform.⁷ The PI will randomly check coach-participant communication weekly to ensure intervention fidelity. IF NECESSARY, the PI will meet with the coaches weekly to discuss challenges and participant communication. Lastly, participants will be given a wireless scale for self-monitoring weight and a Fitbit for self-monitoring sleep (daily minutes) and physical activity (daily steps, minutes). The Fitbit dashboard also allows participants to track dietary calories. Participants will receive instructions on how to sync the scale and Fitbit data with the Sleep GOALS platform. Participants will be asked to weigh themselves in light clothing at least once weekly.⁹

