
Education Control: We used the Pragmatical Model for Comparator Selection in health-related behavioral trials to guide our control group selection.¹⁰ This model suggests utilizing a control group that is not likely to produce a change in the outcome for early-stage intervention development. We considered a no-treatment comparator and wait-list control. Given the timeline and limited resources, we decided a wait-list control is not feasible. We chose an education control because we decided the control should have some value to participants. Therefore, the control group will receive brochures from the American Academy of Sleep Medicine (e.g., sleep hygiene, sleep in women) and SNAP education connection (e.g., family-friendly activities, meal planning) after randomization is revealed.

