9.4.2 ANALYSIS OF THE PRIMARY EFFICACY ENDPOINT(S)

The primary endpoints are the feasibility and acceptability of Sleep GOALS. We will assess the feasibility of the intervention by estimating rates of recruitment, retention, and engagement (i.e., weekly logins; modules completed; daily self-monitoring of diet, physical activity, and sleep; weekly monitoring of weight using point estimates (means or sample proportions) and 95% confidence intervals). We will assess acceptability by estimating rates of satisfaction on various components of the intervention (≥ 4 Acceptability and Feasibility Questionnaire). Our benchmarks for feasibility are similar to those used in the original GOALS Lifestyle intervention. We will use a benchmark of 80% for all feasibility and acceptability measures. To assess the intervention's preliminary efficacy, we will calculate point estimates and confidence intervals for change in weight and PWR. We chose these weight measures as our secondary outcomes since they will be the primary outcome in the future R01. However, we will also explore changes in our proposed behavioral mediators, sleep, diet, and physical activity to inform power calculations for a fully powered study.

We will conduct an exploratory analysis to determine how potential covariates (e.g., parity, breastfeeding

status, postpartum depression, race/ethnicity, relationship status, and employment status) impact the intervention's feasibility, acceptability, and preliminary efficacy. For example, in some studies, breastfeeding is associated with longer nocturnal sleep, but shorter nocturnal sleep in other studies. Collecting data on breastfeeding and other covariates will provide preliminary data on how it impacts the intervention.

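### Section 9.3 puts engagement in the all-randomized population, but only the Sleep GOALS arm is given anything on which engagement can be measured

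*Combined protocol and SAP*

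**What the plan says.** Engagement is part of the primary feasibility outcome. The benchmark table in Section 3 lists modules, weekly self-monitoring and weekly weigh-ins under feasibility; the module criterion is at least "14 (~80%) modules completed within 16 weeks". Section 9.4.2 repeats the classification, naming engagement next to recruitment and retention, and adds: "We will use a benchmark of 80% for all feasibility and acceptability measures".

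Section 9.3 then sets the populations. For feasibility: "For primary outcomes related to feasibility, we will include all randomized participants". For acceptability: "For primary outcomes related to intervention acceptability, we will include all participants randomized to the Sleep GOALS intervention". Engagement is not singled out in either sentence.

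Section 4.1 allocates 20 participants to each arm and describes the comparator: "the control group will receive brochures from the American Academy of Sleep Medicine", together with nutrition and activity leaflets from a second source. The weekly videos, coach, activity tracker and wireless scale are described in Section 4.1 under Sleep GOALS and listed in Section 6.1.1 as its components. Section 6.3 describes login, lesson and self-monitoring counts as the platform's record of compliance with the intervention.

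Section 9.2 gives a 95% confidence interval width of 0.31 in the entire sample, for every feasibility and acceptability benchmark, and 0.44 for estimates within a group.

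**The concern.** Section 9.3 recognises that one primary domain, acceptability, makes sense only in the arm that received the intervention. Engagement has the same property but falls under the all-randomized rule because it is classed as feasibility. An analyst who follows 9.3 must put 20 people in the denominator who had no modules to complete and no study scale to step on, and the plan does not say how to score them.

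Feasibility and acceptability are the trial's primary objective, and engagement is the feasibility component that records use of the intervention. There is no hypothesis test, so the plan's assessment rests on comparing estimates with benchmarks. The denominator can decide whether a benchmark is met.

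**Working it through.** **Inputs.** Arms of 20 and 20 (Section 4.1; blocks of 4 in Section 6.2 give 10 full blocks at 40 participants). Benchmark 80% (Section 9.4.2). Module criterion 14 (Section 3) out of 16 weekly videos (Section 4.3). Stated interval widths 0.31 and 0.44 (Section 9.2).

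**Step 1: reproduce the stated precision.** The Wald full width is 2 × 1.96 × √(p(1 − p)/n). At the worst case p = 0.5:

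- n = 40: 2 × 1.96 × √(0.25/40) = 0.310, stated as 0.31.
- n = 20: 2 × 1.96 × √(0.25/20) = 0.438, stated as 0.44.

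Both figures reproduce. Wilson intervals (0.296 and 0.401) and exact intervals (0.324 and 0.456) do not match. So 0.31 is an n = 40 figure and 0.44 an n = 20 figure.

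**Step 2: follow 9.3 with controls counted as not engaged.** If a fraction e of the Sleep GOALS arm meets a criterion, the reported rate is 20e/40 = e/2, so every result is halved.

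| Sleep GOALS arm | Reported in all randomized | Exact 95% CI |
|---|---|---|
| 20/20 (100%) | 20/40 = 50% | 34% to 66% |
| 16/20 (80%) | 16/40 = 40% | 25% to 57% |

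Reaching 80% of 40 would need 0.80 × 40 = 32 engaged participants, and only 20 could be. Even with perfect engagement, the upper confidence limit of 66% is below the benchmark.

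Section 3 does not say whether the module criterion is a threshold per person or a mean. Read as a mean, the ceiling is (20 × 16 + 20 × 0)/40 = 8 modules, against 14. The conclusion is the same under either reading.

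**Step 3: follow 9.3 with controls treated as missing.** The estimate then comes from the 20 Sleep GOALS participants. The benchmark is met at 16/20 = 80% (exact 95% CI 56% to 94%). That is a sensible analysis, but its population is not the one 9.3 states.

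**Step 4: carry this back to 9.2.** Engagement estimated in the Sleep GOALS arm has n = 20, so its worst-case width is 0.44. Acceptability is already restricted to that arm by 9.3, so 0.31 does not apply to it either. At p = 0.8 and n = 20 the Wald width is 2 × 1.96 × √(0.16/20) = 0.35.

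**The case against.** The strongest reply is that this is loose wording and that no competent analyst would count modules in a brochure arm. The context supports that. The synopsis speaks of engagement with the intervention, Section 9.4.2 of the feasibility of the intervention, and Section 9.2 foresees estimates within a group. Excluding controls would also follow from allocation and from what each arm receives, not from the results, so it leaves little room for data-driven choice. In addition, the pilot is descriptive, and no formal stop/go rule is attached to the benchmarks.

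Most of this stands and limits the consequence. It does not remove the mismatch: Section 9.2 never assigns engagement to the within-group estimates, and its whole-sample figure repeats the all-randomized reading.

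Three stronger readings are tempting and are not supported.

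- A reader might infer that the engagement benchmarks are unattainable under the plan. That holds only if controls are scored as not engaged, and no section says so.
- A reader might infer that analysts are free to drop Sleep GOALS participants who never start or who withdraw. The all-randomized wording of 9.3 forbids this. Section 7.2 allows replacement of those who do not receive the intervention, but it does not remove them from the analysis.
- A reader might infer that the whole feasibility population is wrong. It suits retention and sample composition; the fault is confined to engagement.

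**Conclusion.** Wrong as written, for engagement only. A stated rule, not an omission, gives a primary outcome a denominator in which half the participants have nothing to engage with. With controls counted as not engaged, the rate is capped at 50% and an arm exactly at benchmark is reported as 40%. With controls treated as missing, the analysis is the 20-person arm and departs from the stated population without acknowledgement.

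The figures assume 20 per arm. They also assume that controls have no access to the platform, tracker or scale. The documents do not say this outright; it is inferred from the description of the control arm and from where the components are listed, and no section gives controls any of them.

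The same confusion affects Section 9.2: the width of 0.31 is correct for 40 participants but is claimed for measures that can be estimated in only 20.

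**What to change.** In Section 9.3, split the feasibility population:

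- retention and sample composition: all randomized participants;
- engagement (logins, modules, self-monitoring weeks, weigh-in weeks): all participants randomized to Sleep GOALS.

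In Section 9.2, limit the width of 0.31 to measures taken in the whole sample and state 0.44 (n = 20) for engagement and acceptability.

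A rule that counts modules or weeks after discontinuation as not completed would be a reasonable addition, but it is optional and not needed to cure the mismatch.

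The cost is a small edit in two sections and a less favourable stated precision for engagement and acceptability. No new data are needed.

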9.4 STATISTICAL ANALYSES

9.4.1 GENERAL APPROACH

We will use descriptive statistics for primary and secondary outcomes.

9.4.2 ANALYSIS OF THE PRIMARY EFFICACY ENDPOINT(S)

The primary endpoints are the feasibility and acceptability of Sleep GOALS. We will assess the feasibility of the intervention by estimating rates of recruitment, retention, and engagement (i.e., weekly logins; modules completed; daily self-monitoring of diet, physical activity, and sleep; weekly monitoring of weight using point estimates (means or sample proportions) and 95% confidence intervals). We will assess acceptability by estimating rates of satisfaction on various components of the intervention (≥ 4 Acceptability and Feasibility Questionnaire). Our benchmarks for feasibility are similar to those used in the original GOALS Lifestyle intervention. We will use a benchmark of 80% for all feasibility and acceptability measures. To assess the intervention's preliminary efficacy, we will calculate point estimates and confidence intervals for change in weight and PWR. We chose these weight measures as our secondary outcomes since they will be the primary outcome in the future R01. However, we will also explore changes in our proposed behavioral mediators, sleep, diet, and physical activity to inform power calculations for a fully powered study.

We will conduct an exploratory analysis to determine how potential covariates (e.g., parity, breastfeeding

status, postpartum depression, race/ethnicity, relationship status, and employment status) impact the intervention's feasibility, acceptability, and preliminary efficacy. For example, in some studies, breastfeeding is associated with longer nocturnal sleep, but shorter nocturnal sleep in other studies. Collecting data on breastfeeding and other covariates will provide preliminary data on how it impacts the intervention.

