3 OBJECTIVES AND ENDPOINTS

Primary Outcomes: The primary outcomes are feasibility and acceptability factors relevant to conducting a subsequent efficacy trial, including the feasibility of recruitment, retention, and engagement (Table 5). To determine acceptability, we will ask participants to complete a modified Acceptability and Feasibility Questionnaire¹ post-intervention. The questionnaire asks participants to provide answers on a 5-point scale (1=*don't agree at all* to 5=*totally agree*) to 39 items about the intervention delivery (e.g., logical, understandable), curricula (e.g., was it logical, relevant, instructive), action plans (e.g., useful, easy to follow), and intervention platform (e.g., user friendly). We will also ask about the coaches' effectiveness, overall satisfaction with the intervention, and the likelihood they would recommend it to a friend. Items with an average score of <4 will be flagged for refinement.

We will then conduct 60-minute semi-structured interviews with participants and coaches. The interviews will take place in person (PHB lab) or by video chat at the participant's preference. We will ask participants whether the content was understandable, the recommendations achievable, and what adaptations are necessary to improve low-scoring items. We will ask the lifestyle coach to discuss their experience and provide suggestions for improving the delivery of the material and their workflow. All interviews will be audio-recorded and transcribed by Qual EASE for qualitative analysis. The feedback will be used to refine the intervention's content delivery, coach's workflow, and training manual. Participants will receive \$50 after each assessments and intervention participants will receive a \$25 honorarium for completing the post-intervention interview.

Secondary Outcomes: *Weight* will be measured with a digital scale, with the participant wearing light clothing and no shoes at baseline and post-intervention. We will estimate PWR as the difference in measured weight at post-intervention and self-reported pre-pregnancy weight.

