Weight	Weight change	$> 5\%$ weight loss
	Postpartum weight retention	< 5 kg of weight retention
The primary endpoints will inform factors related to the conduct of the study (i.e., feasibility) and the intervention content and delivery (i.e., acceptability) of the planned larger definitive efficacy trial. The secondary outcomes will provide estimates of the intervention's effects on the primary outcome of the planned larger definitive efficacy trial		

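### The weight outcomes are meant to estimate the intervention's effect, but no between-arm contrast is specified and the meaning of PWR in the analysis is ambiguous

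*Combined protocol and SAP*

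**What the plan says.** - Section 4.1 sets the design: "Participants will be randomized at a 1:1 ratio to Sleep GOALS intervention (n=20) or an education control group (n=20".
- Section 9.4.2, with the same text in the Analysis Plan part of Section 3, gives the analysis of the secondary outcomes: "we will calculate point estimates and confidence intervals for change in weight and PWR". Section 9.4.1 adds: "We will use descriptive statistics for primary and secondary outcomes". Section 9.1 rules out formal hypothesis testing.
- Section 3 defines PWR at one time point: "We will estimate PWR as the difference in measured weight at post-intervention and self-reported pre-pregnancy weight".
- The Section 3 table sets two weight benchmarks: more than 5% weight loss, and less than "5 kg of weight retention". Neither names an arm or a comparator.
- The text closing that table says the secondary outcomes will supply effect estimates for the outcome that is to be primary in the definitive trial.
- Section 9.3 puts all randomized participants in the secondary analysis.
- The exploratory analysis lists "potential covariates (e.g., parity, breastfeeding status" and others. Baseline weight is not among the examples.

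**The concern.** In a two-arm randomized trial, the effect of the intervention is a difference between arms. The plan states that purpose but stops at point estimates of change. Followed literally, it could yield a change within the Sleep GOALS arm, or a change pooled over all 40 participants. Neither is the randomized effect if weight also moves in the control arm, and the protocol allows for that: Section 2.3.2 says people in both arms may benefit from losing weight, and Section 4.2 says the control brochures cover weight loss. Meeting the two cut-offs has the same limit, since they could be met without any effect of the intervention.

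The quoted phrase also leaves open whether PWR is analysed as a change or as a level. Each reading has a defect. As a change, PWR duplicates weight. As a level, it carries whatever each participant retained at entry, and no criterion in Section 5.1 requires retained weight.

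**Working it through.** **1. The plan's own precision figures.** Section 9.2 gives "acceptable precision (i.e., confidence interval width) of 0.31 for all feasibility and acceptability benchmarks for the entire sample and 0.44 for within-group estimates". The Wald width for a proportion at p = 0.5 is 2 × 1.96 × √(0.25/n), which is 0.310 at n = 40 and 0.438 at n = 20. The figures reproduce, but they concern proportions. The documents give no precision, SD or correlation for weight or PWR, so all such inputs below are assumptions.

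**2. What a change estimates.** Let c be the mean change in controls and δ the intervention effect.
- Within the Sleep GOALS arm: δ + c.
- Pooled over both arms at 1:1: (δ + c + c)/2 = c + δ/2.
- Between arms: (δ + c) − c = δ.

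Only the last is the effect. For scale, assume c is 1 to 3 kg in absolute size and baseline weight is 80 to 90 kg. The 5% benchmark is then 4.0 to 4.5 kg, and c is 1/4.5 = 22% to 3/4.0 = 75% of it. If controls lose weight, the within-arm change overstates the effect; if they gain, it understates it.

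**3. PWR read as a change.** With W0 and W16 the baseline and Week 16 weights and P the pre-pregnancy weight, (W16 − P) − (W0 − P) = W16 − W0. P cancels, so this is the weight change in kg.

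**4. PWR read as the Week 16 level.** W16 − P = (W16 − W0) + (W0 − P), which is weight change plus baseline retention. For assumed PWR SDs of 5, 7 and 9 kg, the SE of a chance baseline gap between arms is SD × √(2/20) = 1.58, 2.21 and 2.85 kg. A gap of 2 kg or more in either direction then has probability 0.21, 0.37 and 0.48. Adjusting for baseline PWR multiplies the CI width by about √(1 − ρ²): 0.80 at ρ = 0.6 and 0.44 at ρ = 0.9.

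These figures apply only to the level. Weight change already subtracts baseline weight. With equal variances, ANCOVA relative to a change score has a CI ratio of about √((1 + ρ)/2), or 0.975 at ρ = 0.9, a gain of 2.5%. For weight, the main gain comes from naming the contrast.

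**5. Precision of a between-arm difference.** The 95% half-width is t(0.975, 2n − 2) × SD × √(2/n). The row for 16 per arm reflects the 20% attrition limit (20 × 0.8).

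| SD of weight change (assumed) | 3 kg | 4 kg | 5 kg | 6 kg |
|---|---|---|---|---|
| 20 per arm | 1.92 | 2.56 | 3.20 | 3.84 |
| 16 per arm | 2.17 | 2.89 | 3.61 | 4.33 |

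For the unadjusted PWR level with 20 per arm, the half-width is 3.2 to 6.0 kg (assumed baseline PWR SD 4 to 8 kg, change SD 3 to 5 kg).

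**6. Illustration.** One simulated set of 40 used pre-pregnancy weight with mean 80 and SD 15 kg, baseline retention with mean 6 and SD 6 kg, change SD 4 kg and a true effect of −2 kg.
- Weight adjusted for baseline weight: −1.44 kg (SE 1.12).
- PWR adjusted for baseline PWR: −1.44 kg (SE 1.12).
- PWR unadjusted: −1.37 kg (SE 1.82).
- Adjusting for both baseline and pre-pregnancy weight, the weight and PWR estimates are identical: −1.444 kg (SE 1.131).
- 23 participants met the PWR cut-off; only 9 of those also lost more than 5%.

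An adjusted PWR contrast therefore nearly repeats the weight contrast.

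**The case against.** The strongest reply is that this is a pilot with feasibility as its primary outcome, a descriptive analysis and no hypothesis tests, and that the arm contrast can be computed from the planned data. That limits the severity. It does not close the gap, because a difference with a CI needs no test and is what Section 3 says the outcomes are for.

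Four stronger readings go further than the documents support:
- **That the plan discards the control arm.** Section 9.3 includes all randomized participants, and Section 4.1 explains that the comparator was chosen as unlikely to change the outcome. The contrast is unspecified, not excluded.
- **That PWR is a duplicate outcome.** The identity in step 3 is exact, but Section 3 defines PWR only after the intervention, its benchmark is a level, and the synopsis names retention as the endpoint. The level is the likelier reading.
- **That the baseline-gap and CI-narrowing figures show a fault in the weight analysis.** They hold only for the PWR level and cannot be combined with the duplicate reading.
- **That a biased mean will set the size of the larger trial.** Section 9.2 says estimates of variability will guide that calculation. A common shift in weight does not by itself bias an SD of change.

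**Conclusion.** The point holds. The weight analysis lacks the between-arm contrast that its stated purpose requires, its benchmarks have no comparator, and the wording on PWR needs one clear reading. Its size cannot be fixed from the documents. The 22% to 75% range assumes a control change of 1 to 3 kg and weights of 80 to 90 kg, and the direction could be either. The 21% to 48% chance of a 2 kg baseline gap assumes a PWR SD of 5 to 9 kg and concerns the level only. The recommended estimate would itself be imprecise: a half-width of about 1.9 to 3.8 kg with 20 per arm, for an assumed change SD of 3 to 6 kg. It should be corrected, as a moderate point.

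**What to change.** 1. In Sections 3 and 9.4.2, make the secondary estimate the between-arm difference in Week 16 weight with a 95% CI, from ANCOVA adjusting for baseline weight. No test is needed. Adjustment for weeks since delivery is optional.
2. State that PWR is the Week 16 level and describe it by arm. If a between-arm PWR difference is shown, adjust it for baseline PWR and note that it nearly duplicates the weight contrast.
3. Report the proportions with more than 5% loss and with less than 5 kg retained by arm, as description only.
4. Remove parity from the covariate list, since Sections 5 and 5.1 admit only primiparous participants.

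The cost is wording. Baseline weight is already measured, and Section 3 already relies on self-reported pre-pregnancy weight. No extra participants or visits are needed.
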